A key issue in many settings, including ours, is that testing falls into a separate budget from the treatment of patients with CDI infections. This has the potential to distort the decision of whether to run a test and, if so, what sort of test. The distortions are of two types. First, the hospital may decide to order more tests than is optimal, since the tests are perceived as "free" from the perspective of decision-makers. At the same time, the diagnostic facility may choose low-cost, slow diagnostics, because the costs associated with delays in test results are borne by the hospital. This is a classic case of silos in health care costs inefficiently distorting policy decisions, with potentially negative results for both patient health and costs.

Many institutions follow the clinical practice guidelines provided by the Infectious Diseases Society of America for the management of *C. difficile* (Cohen et al., 2010). As part of routine Infection Prevention and Control (IPC) management, patients with acute diarrhea of unknown cause are pre-emptively placed in private rooms with additional contact precautions, which mandate the use of gowns and gloves for healthcare workers. This is also known as patient isolation. Investigation for gastrointestinal pathogens is typically initiated and the duration of patient isolation depends largely on the result of microbiological testing. When severe or complicated CDI is suspected, patients are initiated on empiric treatment as soon as the diagnosis is suspected. Generally, oral metronidazole is used for mild-to-moderate CDI and oral vancomycin for severe CDI. Among hospitalized patients with acute diarrhea, initiation of pre-emptive management for CDI is common. With requested CDI screening, 85% are negative on GDG screen and 89% are negative post PCR confirmation.

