This study is a cross-sectional CRXO in that, each cluster-period consists of different individuals (patients). The order in which the interventions are delivered to each cluster (ward) is randomized to control for potential period effects. Within Foothills Hospital there are 40 wards which will be observed over a 12-month period. Each ward is randomly assigned to administer one of the two interventions for the first 6-month period (Period 1). In the second 6-month period (Period 2), the ward will administer the other intervention. Within each ward (cluster) there are two cluster-periods. Study outcomes during Period 1 and Period 2 intervention will be compared in both arms (NPT and centralized laboratory testing).

NPT testing can deliver results within several hours, while typically off-site testing takes one to two days. If NPT and the off-site testing deliver identical test results as our pilot data suggest, we can follow the clinical outcomes for each arm without the confounder of differences in test performance. As a contingency, if variation in test performance characteristics is found, analysis of patient outcomes will take this into consideration.

For patients without CDI, the antibiotics, and in many cases, the isolation, are unnecessary. NPT testing has the potential to avoid this unnecessary use of antibiotics and to avoid costly isolation procedures for the day+ that standard testing requires. It also enables a better-directed diagnostic process for the cause of diarrhea. For patients who are positive for CDI, the earlier test result will influence downstream events such as initiation of antibiotic therapy, resolution of disease, hospitalization days, and other clinical outcomes.

We hypothesize that NPT for CDI will result in reduced patient isolation days in the hospital, decreased morbidity and mortality, reduced unnecessary antibiotic use and overall reduced costs to the health care system, including both hospital and laboratory.

Previous data has indicated that the mean number of patients a ward is 39/month ($SD=43$) for a total of 1578 patients in a 6-month period and the mean number of negative patients is 33/month ($SD=34$) for a total of 1300 negative pts in a 6-month period. The inclusion criteria will be diarrhea in adult patients admitted to four acute care hospitals in the Calgary region being tested for CDI. Outpatients and patients in the emergency room will be excluded.

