Our primary endpoint is to examine the differential effect of NPT on the duration of contact precautions (i.e. patient isolation days). Secondary outcomes will compare turn-around times from specimen submission to result, days of hospitalization, the number of days of antibiotic therapy, the incidence of CDI, severe CDI, and in-hospital mortality. A comprehensive economic evaluation will be performed to determine the cost of testing, patient isolation, and hospitalization for all patients in the control and treatment arms.

Methods:

Contact precautions (i.e. patient isolation) due to CDI will be defined as an order by healthcare workers for contact precautions within the 7-day infection window of a CDI diagnosis. The length of time on contact precautions will be defined as the calendar date contact precautions are completed or patient discharge date minus the calendar date contact precautions are ordered. Data on contact precautions will be extracted from the clinical patient management system in Calgary, known as Sunrise Clinical Manager (SCM). It is used extensively in all Calgary acute care facilities and emergency departments. These data include patient identifiers (e.g. patient health number, names, date of birth), start and stop dates of isolation, facility, and patient care unit where isolation order was placed, and reason for isolation (e.g. CDI, diarrhea). These data will be linked to the specimen results tested for CDI by the patient's Personal Health Number (PHN). Turn-around times from specimen submission to result will be provided by Calgary Laboratory Services. Days of hospitalization will be defined as the difference between the admission and discharge date. The specimen results will be linked to the Discharge Abstract Database using the patient's PHN to determine during which acute care encounter the specimen was collected and the admission/discharge dates of that encounter. Antibiotic therapy will be defined as the administration of antibiotics initiated on the day of and up to 48 hours after specimen collection for CDI testing. Total days of antibiotic therapy during the acute care encounter will be defined as the calendar date antibiotic therapy is completed minus the calendar date antibiotic therapy is ordered. The data will be extracted from SCM.

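### Antibiotic days are counted as completion date minus order date, so a same-day course can score 0; if NPT prevents starts and untreated patients count as 0, the measured saving is understated

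*Combined protocol and SAP*

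**What the plan says.** Study Objectives lists "the number of days of antibiotic therapy" among the secondary outcomes. Methods decides which courses count: the "administration of antibiotics initiated on the day of and up to 48 hours after specimen collection for CDI testing". It then measures their total length as the "calendar date antibiotic therapy is completed minus the calendar date antibiotic therapy is ordered", with data taken from the hospital's clinical management system (SCM). It adds no day and sets no one-day minimum for a treated patient. It does not say whether completion is the last treated date or the first date without drug, or what score an untreated patient receives. No outcome records whether antibiotics were started at all.

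The expected benefit is in patients without CDI. Study Objectives says that "NPT testing has the potential to avoid this unnecessary use of antibiotics", and gives the reason: "NPT testing can deliver results within several hours, while typically off-site testing takes one to two days". Background and Significance adds that "initiation of pre-emptive management for CDI is common" and that, of those screened, "89% are negative post PCR confirmation".

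**The concern.** A result within hours can act on antibiotic use in two ways: it can stop an empiric course sooner, or it can prevent the course from starting. Subtracting dates treats the two differently. If the completion date is the last treated date, one treated day is lost from each course. The loss occurs once per treated patient, not once per enrolled patient, so it cancels between arms only when the share treated is the same.

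The shortest courses lose the largest fraction of their length, and short courses in CDI-negative patients are what fast reporting would be expected to produce or prevent. With no start (yes/no) outcome beside it, the day count would be the only place where prevented courses could show. At stake is the size of one secondary effect and the reported level of antibiotic use in both arms.

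**Working it through.** The plan gives no effect size, start rate or course length for this outcome, so there is no stated figure to reproduce. The check is date arithmetic.

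**Inputs from the document:** the subtraction rule and the 48-hour window (Methods); reporting times, and the count of CDI-negative patients, "for a total of 1300 negative pts in a 6-month period" (Study Objectives).

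**Assumptions, not in the document:** completion is the last treated date; the first dose is on the order date; untreated patients score 0; start shares and course lengths are as shown.

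**Step 1, one course.** A course on L calendar dates scores L − 1 by the plan's rule and L by an inclusive count.

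| Dates covered (L) | Plan's rule | Inclusive | Credit lost if this course is prevented |
|---|---|---|---|
| 1 | 0 | 1 | 100% |
| 2 | 1 | 2 | 50% |
| 3 | 2 | 3 | 33% |
| 5 | 4 | 5 | 20% |
| 10 | 9 | 10 | 10% |

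**Step 2, arm means.** Let p be the share started and m the mean date difference among treated patients (C = central, N = NPT).

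- Saving by the plan's rule: pC·mC − pN·mN.
- Inclusive saving: pC·(mC + 1) − pN·(mN + 1).
- Shortfall: the second minus the first = pC − pN, in days per patient. It does not depend on course length.

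The regression in Data Analysis does not remove it. Least squares is linear in the outcome, so the testing coefficient for inclusive days equals the coefficient for the plan's score plus the coefficient for a 0/1 indicator of having started.

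**Step 3, illustration** with mC = 1.5 and mN = 0.2.

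| Started, C vs N | Inclusive saving | Plan's rule | Shortfall |
|---|---|---|---|
| 30% vs 30% | 0.75 − 0.36 = 0.39 | 0.45 − 0.06 = 0.39 | 0 |
| 30% vs 28% | 0.75 − 0.336 = 0.414 | 0.45 − 0.056 = 0.394 | 0.02 (5%) |
| 30% vs 20% | 0.75 − 0.24 = 0.51 | 0.45 − 0.04 = 0.41 | 0.10 (20%) |
| 30% vs 15% | 0.75 − 0.18 = 0.57 | 0.45 − 0.03 = 0.42 | 0.15 (26%) |

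If these shares applied to the 1300 negative patients, the shortfalls would be 0.02 × 1300 = 26, 0.10 × 1300 = 130 and 0.15 × 1300 = 195 treated days. The percentages depend on the assumed m; the shortfalls in days do not. A mean of 0.2 is credible only for CDI-negative patients. The roughly 11% who are positive (100% − 89%) would lengthen the average course and shrink the percentages.

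**Step 4, where the effect vanishes.**

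- NPT only shortens courses, for example from 3 dates to 1 in 40% of both arms: inclusive 0.4 × 3 − 0.4 × 1 = 0.80; plan's rule 0.4 × 2 − 0.4 × 0 = 0.80.
- Only treated patients are analysed: (mC + 1) − (mN + 1) = mC − mN. The missing day falls out as a constant.
- SCM records the first drug-free date as completion: the subtraction already gives L.

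**The case against.** The strongest reply is that date subtraction is a recognised convention and Methods uses it for isolation and hospital stay too. As a measure of elapsed time it is unbiased on average: if start times are spread evenly over the day, a 6-hour course crosses midnight with probability 0.25, so it scores 0.25 day on average, against 1.25 by the inclusive count. This stands. The shortfall exists only if the target is treated calendar days, and the plan never says which it means.

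The other premises are also open. The plan gives no score for untreated patients. An order dated before the first dose would offset the loss. The documents refer to avoiding unnecessary use, not specifically to preventing starts. Since pre-emptive management is described as common and NPT still takes hours, NPT might shorten courses without changing how many begin.

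A reader might therefore infer more than the text supports: that the subtraction is simply an error, that it must understate the saving, or that 20% to 26% of the effect is lost. The documents establish none of these. They leave the target and the dates undefined and supply no rates from which a percentage could be derived.

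What survives is narrower. Under the natural reading of a completion date, a same-day course receives 0, and no other outcome in the plan would show the difference between that patient and one never treated.

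**Conclusion.** The point holds conditionally. The measured saving in treated days is understated by (share started in central − share started in NPT) × 1 day if three things are true: completion is the last treated date, untreated patients are analysed as 0, and NPT lowers the share started. If the third fails because NPT only shortens courses, or if only treated patients are analysed, the arm difference is not biased by this rule, though antibiotic use is understated in both arms. Analysing treated patients alone is no remedy, because prevented courses then earn no credit at all.

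The illustrative size is 0.02 to 0.15 day per patient over the start shares tried. The true size cannot be fixed from the documents. Under these conditions the bias runs against the trial's hypothesis. It touches one secondary outcome and leaves the primary endpoint alone. The economic evaluation, as described, lists testing, isolation and hospitalization costs, so nothing stated there carries it forward. It is a modest point that is worth settling before the variable is derived.

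**What to change.** 1. If SCM holds administration dates, define antibiotic days as the number of calendar dates with at least one administered dose among qualifying courses.
2. Otherwise use completion date minus start date plus 1 for treated patients, after confirming that SCM's completion date is the last treated date. If it is the first drug-free date, keep the subtraction and say so.
3. State that untreated patients score 0 and that all tested patients stay in the comparison.
4. Report the proportion ever started on antibiotics by arm beside the day count, so that prevented courses and shortened courses can be told apart.

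The cost is a check of the SCM date fields and a change to one derived variable. The drawback is a slight overcount under item 2 when the order precedes the first dose and only order dates are available.

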The intervention of interest is implementing a new RDT to Near Patient Testing (NPT); screening for CDI to be performed at the hospital rapid response laboratory (RRL) instead of the DSC. Techlab Inc. offers a lateral flow assay (C. DIFF QUIK CHEK COMPLETE® test) that detects both GDH and Toxin simultaneously and further simplifies the testing algorithm. As prescribed in the two-step algorithm, GDH and Toxin negatives will be reported out immediately as negative for CDI, while positive or discrepant results will be confirmed at the DSC using NAAT. The vast majority of requests for CDI testing are negative thus allowing a majority of results to be reported immediately to patient wards without NAAT confirmation at the DSC.

Study Objectives:

Calgary presents a unique opportunity to examine the effect of decentralizing CDI testing to Near Patient Testing. While it is not possible to perfectly duplicate the testing technology (described earlier) at NPT and the central laboratory, it is possible to provide equivalent testing. In a pilot study, we tested 20 stool samples by our current CLS centralized testing algorithm and anticipated NPT algorithm. Both algorithms rely on a two-step approach, namely GDH screen and molecular confirmation for toxin although the platforms are different. We had 100% concordance in the final result (presence of toxin) between the two algorithms. Further confirmation of this assumption (equivalence in performance) will be completed with a larger sample size prior to finalization of the NPT algorithm.

We will conduct a two-period, two-intervention, cluster randomized crossover (CRXO) design study at Foothills Hospital. Each cluster (ward) will receive each of the two interventions in a separate 6-month period of time leading to two “cluster-periods” with associated “wash-in” and “wash-out” periods attached. The interventions are RDT using NPT for CDI, and testing for CDI using centralized testing at the DSC.

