We will also account for the severity of CDI. The epidemiological definition for severe CDI is that primarily proposed by Cohen *et al*. This definition has been used by infectious disease specialists in Alberta to guide the management and treatment of patients with CDI. Patients with severe CDI will have leukocytosis with a white blood cell (WBC) count $>15,000$ cells/ μ L OR an elevated serum creatinine (i.e. 200 μ mol/L or greater). The inpatient laboratory results that will be considered to meet the definition for severe CDI will be those collected within a 7-day infection window around the date the laboratory tested positive for *C. difficile*. The presence of either measure meeting the criteria within the defined infection window will qualify as meeting the definition of severe CDI. If either criterion is measured more than once during the infection window, the highest value will be used to represent the severity of CDI. The laboratory values will be provided by Calgary Laboratory Services and linked to the positive *C. difficile* test results. In-hospital, all-cause mortality will be defined as death occurring during the acute care encounter where specimens were collected for *C. difficile* testing.

We predict that, given the large number of patients and randomized study design, matching of patients by age, gender, and co-morbidities is not required. Potential hurdles in the study model are logistical challenges associated with building a testing and reporting system for a hospital on a 24hrs/7 days per week basis. The strength of the proposal lies in the scale and nature of the study which seeks to establish the medical and economic benefit of NPT versus centralized testing. The results could dramatically influence public health policy in this country and seek to bridge traditional silos, namely the laboratory and hospital budgets. Data on costs will be furnished by our partners at Calgary Laboratory Services and Alberta Health Services (Infection Prevention and Control).

Data Analysis:

In order to make the data generalizable to other settings, an appropriate econometric methodology to assess the impact of the impact of the NPT testing through multivariate regression is required. For example, consider the following potential model:

$$y_i = \beta_0 + \beta_1 POCT_i + \beta_2 Z_i + \beta_3 H_i + \beta_4 T_i + u_i$$

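### The 7-day windows for severe CDI and for qualifying isolation orders hang on result-dependent dates that the intervention can move, so ascertainment may differ by arm

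*Combined protocol and SAP*

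**What the plan says.** The Methods section sets two 7-day windows.

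- **Severe CDI** (a secondary outcome). The qualifying white-cell and creatinine results are those "collected within a 7-day infection window around the date the laboratory tested positive". If a measure is repeated in the window, "the highest value will be used to represent the severity of CDI".
- **Contact precautions** (the primary endpoint is their duration). They count as due to CDI when there is "an order by healthcare workers for contact precautions within the 7-day infection window of a CDI diagnosis". The plan does not say what dates the diagnosis. Duration then runs from the order date to the completion or discharge date.

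Neither window has a stated number of days before and after its anchor.

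On timing, Study Objectives says that "NPT testing can deliver results within several hours, while typically off-site testing takes one to two days", and adds: "For patients who are positive for CDI, the earlier test result will influence downstream events". It also says that, under near-patient testing (NPT), "positive or discrepant results will be confirmed at the DSC using NAAT", the DSC being the central laboratory. Timing is itself an outcome: "Secondary outcomes will compare turn-around times from specimen submission to result".

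Elsewhere in the Methods the plan uses a different anchor. Antibiotic therapy is what is "initiated on the day of and up to 48 hours after specimen collection for CDI testing", and mortality is tied to the encounter in which specimens were taken.

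**The concern.** A window that decides which data count towards an outcome should start from a date that the randomised intervention cannot change. The date of a positive result is not such a date here, because time to result is what the two arms are meant to differ on. Two identical patients sampled on the same day could have their windows placed on different clinical days because their wards were in different arms.

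For severe CDI this matters because the highest value in the window decides the classification, so adding or dropping a day at either end can change it. Severity also appears among the patient covariates in the example regression under Data Analysis, although that model is offered only as a possibility.

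For contact precautions the stake is narrower. The window decides whether an order qualifies. It does not change the duration of an order that does.

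**Working it through.** The plan gives no figure to reproduce on this point. The check sets the definitions side by side, bounds the shift, and asks what it could do.

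**Step 1. Can the arm move the anchor?** Collection precedes the result, so turn-around cannot move it. The laboratory positive date follows the result. A diagnosis date, if it is taken from the laboratory, does too. No passage moves either window back to collection.

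**Step 2. How large could the shift be in positives?** The plan does not say which date counts as positive.

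- *Local rapid-test date in the NPT arm, central date in the other:* several hours against one to two days, so a shift of about 1 to 2 days.
- *Central NAAT date in both arms:* about 0 days, because NPT positives also go to the DSC.
- *Possible reversal:* the Background describes the central two-step algorithm as needing NAAT only for GDH-positive, toxin-negative specimens, whereas Study Objectives sends all positive or discrepant NPT results for NAAT. A central toxin-positive specimen could then be dated earlier than its NPT counterpart.

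**Step 3. Share of the window not common to both arms** = shift / window length. The width is undefined, so two readings are shown.

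| Shift | 7 days in total | Plus/minus 7 days (15 calendar days) |
|---|---|---|
| 0 days | 0/7 = 0% | 0/15 = 0% |
| 1 day | 1/7 = 14% | 1/15 = 7% |
| 2 days | 2/7 = 29% | 2/15 = 13% |

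**Step 4. How many patients?** The severity window applies only to positives. With 1578 tested patients per 6-month period (Study Objectives) and 89% negative after PCR (Background), 1578 × 0.11 = 174. From the plan's own counts, 1578 − 1300 = 278. The negative share is therefore 1300/1578 = 82% to 89%.

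**Step 5. What could the shift do to the severe share?** This is an illustration on assumed inputs, with identical patients and no true effect. White cells are measured daily. The peak (in thousands) is lognormal with median 12 and log-SD 0.4, falling 1.5 per day on either side. The peak day is normal with SD 2 around the mean shown. Severe means a highest value above 15.

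| Mean peak relative to collection | Window | Anchor at day 0 | Day 1 | Day 2 | Change, day 0 to 2 |
|---|---|---|---|---|---|
| 2 days before | ±3 days | 24.6% | 22.6% | 19.7% | about −5 points |
| At collection | ±3 days | 26.1% | 25.8% | 24.7% | −1.4 points |
| 2 days after | ±3 days | 24.6% | 25.7% | 26.1% | +1.5 points |
| Any of the three | ±7 days | – | – | – | under 0.3 points |

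Both size and sign depend on the assumed trajectory and window width, which the documents do not give.

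**Step 6. Isolation orders.** Assume a plus/minus 3-day window and an order placed two days before collection. If the result comes on the collection day, the order is at day −2 and qualifies. If it comes two days later, the order is at day −4 and does not. An order placed on the collection day is at day 0 or day −2 and qualifies either way.

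**The case against.** The strongest reply is that the one-to-two-day difference is a general statement about results, while the severity window concerns positives only. NPT negatives are reported at once; NPT positives go to the DSC for NAAT. If that confirmation is what dates a positive, the shift may be near zero. This stands, and it is why the range has to start at 0. It does not remove the point, because the plan does not name the date that counts.

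A reader might take 14% to 29% as the size of the bias. The documents do not support that. Those figures are shares of calendar days under one reading of the window and one reading of the positive date.

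A reader might also infer that the primary endpoint is biased. That goes too far. The contact-precautions window refers to an undated diagnosis and is not expressly the same window as the one for severity. It governs only whether an order qualifies. The Background says patients with unexplained acute diarrhea are isolated pre-emptively, so orders placed close to collection would stay inside even a plus/minus 3-day window. And 82% to 89% of tested patients are negative, with no positive date to shift.

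Finally, the date of testing positive could loosely mean the date of the positive specimen, in which case nothing moves by arm. This reading is possible but weaker, since the plan names specimen collection where it means it, in the antibiotic definition.

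**Conclusion.** The point holds as a risk that the definitions leave open. The severity window is tied to a date that the intervention can move, and the contact-precautions window to one that it may move, so ascertainment of severe CDI, and possibly which orders qualify in CDI-positive patients, may differ by arm without any difference in patients. The documents do not show that it will differ.

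The shift in positives lies between about 0 days (or a reversal) and 1 to 2 days, which is 0% to 29% of a 7-day window or 0% to 13% of a plus/minus 7-day window. This rests on the plan's own turn-around figures and on two readings of an undefined width. The effect on the severe share is unknown in size and sign, and could be negligible if the window is wide. It concerns roughly 174 to 278 positives per 6-month period. The change is still worth making, because it replaces a stated rule with a safer one that the plan already uses elsewhere.

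Negative patients have no diagnosis date at all, so the contact-precautions definition is unclear for most tested patients. That is a separate question and not part of this point.

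**What to change.** In the Methods, in both the contact-precautions and the severe-CDI definitions, anchor the 7-day window on the collection date of the first positive specimen in both arms. State how many days before and after that date are included, identically for each arm. Re-anchoring alone is not enough, because the width largely determines how much a shift matters.

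With this change the shift caused by turn-around time is 0 days and the non-shared part of the window is 0%. It is a free improvement: the antibiotic definition already needs the collection date, so no new data and no change to trial conduct are required. Reporting turn-around time separately for positives, from data already planned, would also show how large the shift would have been.

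### Mortality is counted only until discharge, so if near-patient testing (NPT) shortens stay, fewer deaths can be counted under NPT with no change in the risk of dying

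*Combined protocol and SAP*

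**What the plan says.** Study Objectives states the hypothesis: "We hypothesize that NPT for CDI will result in reduced patient isolation days in the hospital, decreased morbidity and mortality". The secondary outcomes in the same section include "days of hospitalization, the number of days of antibiotic therapy, the incidence of CDI, severe CDI, and in-hospital mortality", so length of stay and mortality are both compared between arms.

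Methods defines the two outcomes so that they share an endpoint. For mortality: "In-hospital, all-cause mortality will be defined as death occurring during the acute care encounter where specimens were collected for *C. difficile* testing". For stay: "Days of hospitalization will be defined as the difference between the admission and discharge date". The specimen results are linked by Personal Health Number (PHN) to the Discharge Abstract Database "to determine during which acute care encounter the specimen was collected and the admission/discharge dates of that encounter".

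On the link between testing and stay, Study Objectives says of CDI-positive patients that "the earlier test result will influence downstream events such as initiation of antibiotic therapy, resolution of disease, hospitalization days, and other clinical outcomes". It gives neither direction nor size. On timing of results it says: "NPT testing can deliver results within several hours, while typically off-site testing takes one to two days".

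The documents set no fixed follow-up from the specimen, name no source for deaths after discharge, and do not treat live discharge as a competing event. The model in Data Analysis gives isolation hours and hospital days as example outcomes and does not take up mortality.

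**The concern.** A mortality count that closes at discharge compares like with like only if discharge timing is the same in both arms. Here discharge timing is an outcome that the intervention may change. If patients leave sooner under NPT, any deaths that would have fallen on the removed days move outside the count. Randomizing wards does not protect against this, because the difference in observation time arises after randomization.

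The mortality hypothesis is what is at stake. If fewer in-hospital deaths were seen under NPT together with shorter stays, the planned data could not separate a lower risk of dying from earlier discharge. Deaths after discharge, or in a later admission, would be missing from both arms, and more of them from the arm with the shorter stay.

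**Working it through.** The plan gives no mortality rate, length of stay or expected effect on either, so there is no stated figure to reproduce. What follows is an illustration.

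**Inputs from the documents**
- Patients tested per period: previous data are given "for a total of 1578 patients in a 6-month period". In a two-period crossover this is also roughly the size of one arm. The monthly ward mean beside it does not multiply up to this total (39 × 6 × 40 = 9360, whereas 39 × 40 = 1560), so I use the total only for scale.
- CDI-positive share, Background and Significance: 89% negative after PCR, so 11% positive.
- CDI-positive share, Study Objectives: (1578 − 1300)/1578 = 278/1578 = 17.6%.

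**Assumptions, not in the documents**
- Daily death hazard h = 0.005, constant and equal in both arms.
- Mean time from specimen to discharge, in the absence of death, m = 10 days under central testing, with a constant discharge hazard 1/m.

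**Step 1. Stay shortened in every patient.** Counted in-hospital mortality = h/(h + 1/m) = hm/(1 + hm).

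| m (days) | Counted mortality | Ratio to m = 10 |
|---|---|---|
| 10 | 0.0500/1.0500 = 4.76% | 1.00 |
| 9 (1-day cut) | 0.0450/1.0450 = 4.31% | 0.90 |
| 8.1 (1.9-day cut) | 0.0405/1.0405 = 3.89% | 0.82 |

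With 1578 patients, the 1-day cut takes the count from 75.1 to 68.0, about 7 fewer deaths at the same risk of dying. Doubling h to 0.01 hardly changes the ratio: 8.26%/9.09% = 0.91.

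**Step 2. Stay shortened only in CDI-positive patients**, the group for which the documents mention stay. Let p be the positive share and r the ratio from step 1, with the same mortality in positives and negatives under central testing. Overall ratio = 1 − p(1 − r).
- 1-day cut (r = 0.904): p = 0.11 gives 1 − 0.11 × 0.096 = 0.989; p = 0.176 gives 1 − 0.176 × 0.096 = 0.983. That is about 1 death in 1578 patients.
- 1.9-day cut (r = 0.817): 0.980 and 0.968, or about 1.5 to 2.4 deaths.
- If positives died at twice the rate of negatives, they would supply 0.22/1.11 = 20% to 0.352/1.176 = 30% of deaths. The 1-day ratio would then be about 0.98 to 0.97.

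**Step 3. Lower hazard near discharge.** Patients about to leave are probably at lower risk than the average inpatient. If the hazard on the removed days is a fraction f of average, the ratio is approximately 1 − f × cut/stay. For a 10-day stay and f between 0.1 and 0.5:
- a 1-day cut in all patients gives 0.99 to 0.95;
- a 2-day cut in all patients gives 0.98 to 0.90.

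Confining the cut to positives moves these closer to 1 again.

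**Step 4. Fixed window.** If every death to day 30 is counted wherever it occurs, equal hazards give 1 − exp(−0.005 × 30) = 13.9% in both arms. The ratio is 1.00 whatever the discharge date.

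**The case against.** The strongest reply is that the premise is an inference. A reader might conclude that the trial predicts shorter stays under NPT, and hence that its mortality comparison is biased in NPT's favour. The documents do not go that far. They say stay will be influenced, without direction, and only for CDI-positive patients. The hypothesis does not list length of stay, and naming stay as a compared outcome is not a prediction. If stay does not differ, this artefact does not arise.

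A reader might also take the ratio of 0.90, or 0.82, as the likely size. That applies the cut to every patient. For patients without CDI, the protocol names antibiotics, isolation and a better-directed work-up, not stay. Positive or discrepant screens still go off-site for confirmation, so positives may not gain the whole time saving. Nothing in the documents says that discharge moves by the full testing delay.

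Nor do the documents describe early discharge after a false-negative result, or call mortality a safety outcome. It is one of several secondary outcomes, and the analysis is to take account of any difference in test performance. Reading the definition as hiding harm of that kind therefore goes beyond the text.

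These points stand, and they limit the size. They do not repair the definition. It still closes at an event the intervention may move, while a mortality benefit is hypothesized. An effect on stay in negatives is unstated but not excluded. The term in-hospital mortality is used consistently, but that does not make it a suitable measure for this hypothesis.

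**Conclusion.** The point holds in conditional form. If NPT shortens stay and there is some risk of death on the removed days, fewer deaths will tend to be counted under NPT at an unchanged risk of dying. Deaths after discharge or in a readmission are not counted in either arm.

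The size cannot be fixed from the documents. On the assumed hazard and stay, a 1-day cut gives about 0.90 if it applies to all patients and about 0.98 to 0.99 if it is confined to positives. A lower hazard near discharge brings either figure nearer to 1. The bias may therefore be small, and it affects a secondary outcome. The change is worth making because it is cheap and because the artefact, where it occurs, runs in the direction of the hypothesized benefit.

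**What to change.** Add all-cause death within a fixed window from index specimen collection, the same in both arms, and name it as the outcome for the mortality hypothesis. Thirty days is an example; the team should choose the window and state it in advance. Obtain the deaths by PHN linkage to later encounters in the Discharge Abstract Database, and to death records if these are available. Keep in-hospital death as a descriptive outcome, which also retains in-hospital deaths after the window closes.

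If only hospital records can be used:
- count deaths in any acute care encounter up to the chosen day;
- report live discharge as a competing event;
- state that out-of-hospital deaths are missed, so the bias is reduced but not removed;
- do not claim reduced mortality from in-hospital deaths alone.

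Adjusting the existing outcome for length of stay is not a substitute, because stay may itself be affected by the intervention.

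The cost is one added definition, a wider query on a database already being linked, a short wait for the last patients to complete the window, and possibly one more data request for deaths outside hospital.
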